Based on previous data, we anticipate that we will be able to identify at least 50 adolescents per clinic for a total of at least 5000 adolescents. Assuming a prevalence of 60%, an intra-class coefficient (ICC) of 0.05 and a clinic size of 50 we would need to select 102 clinics for estimating the expected proportion with a 2.5% absolute precision and 95% confidence. With a sample size of 5,000 adolescents who are enrolled in HIV care during the previous 12-24 months, the precision of the estimates across possible ranges (50%-90%) of prevalence of retention in care or viral load suppression will range from $\pm 2.6\%$ to $\pm 1.5\%$ (Table 5). Thus, with 5000 adolescents or more, our study will have high precision in estimating the prevalence of retention in care and HIV viral load suppression, providing valuable input for understanding impact of interventions aimed at improving these adolescent HIV outcomes.

Table 7: Precision estimates for prevalence of retention and viral load suppression in HIV-infected adolescents

Indicator	Adolescents evaluated	Observed Prevalence	Events	CI	Precision
Retention or suppressed viral load	5000	50%	2500	47.4-52.6%	+/-2.6%
	5000	60%	3000	57.5-62.5%	+/-2.5%
	5000	70%	3500	67.6-72.4%	+/-2.4%
	5000	80%	4000	77.9-82.1%	+/-2.1%
	5000	90%	4500	88.5-91.5%	+/-1.5%

Aim 2: Given that the goal of the interviews conducted in this aim is to gather information on experiences with disclosure and transition and use this information to refine study tools, we believe that conducting 16 focus group discussions with adolescents (N=96), 16 focus group discussions with primary caregivers of adolescents (N=48), 38 interviews with HCWs and 30 interviews with administrators and policy makers, will give us adequate numbers to reach our study goal and enough diversity in experiences to ensure different perspectives are accurately represented in study tool refinement. A working group comprised of approximately 40 HCWs with significant expertise in providing care for HIV-infected children, adolescents and adults will be

sufficient to foster rich discussions around study tools. Including approximately 40 HCWs, will allow participation of all stakeholders.

Aim 3: For the RCT, using a conservative estimate of 20% of clients being between 10-24 years old and each clinic having at least 500 active clients, we anticipate 200 eligible clients per clinic, for a total of 1000 eligible clients per randomization arm.

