- We assume that 100 of these eligible clients will be aged 6-15 and that the rate of complete disclosure will be 15% in the control clinics based on our prior studies and the literature with increased prevalence per year of age in this age-window.
- We assume that 100 of these eligible clients will be aged 15-24 years and that 20% (n=20) will be receiving care in a pediatric program and could be eligible to transition (200 per RCT arm). During 2-year follow-up, we anticipate that in the control arm 20% will transition and 10% will transition effectively.

With 10 intervention and 10 control sites, we will have sufficient power to detect an increase in proportion of adolescents with disclosure from 30% to 50%, an increase in proportion who initiate transition from 50% to >80%, and an increase in proportion with effective transition from 10% to 20%. This assumes alpha of 0.05, 80% power, and a conservative estimate of the coefficient of variation of 0.3 (Table 6). Heterogeneity between clusters is expected to decrease with control for baseline testing rates, leading to increased power beyond that which is noted above.

Table 8: Power and sample size ranges

	Outcome Control	Outcome Intervention	Number of clinics per RCT arm to detect difference
Age 10-15	N=1000 (100/clinic)	N=1000 (100/clinic)	
Disclosure process started (proportion)	50% 50% 50%	>80% >90% 100%	9 6 5
Disclosure complete (proportion)	30% 30% 30%	50% 70%	8 4 3
Disclosure age median	14 years old	12 years old	NA
24-month LTFU	20%	10%	7
Age 16-24	N=1000 (100/clinic)	N=1000 (100/clinic)	
Transition discussed (proportion)	20% 20% 50%	40% 60% 100%	6 3 5
Transition complete (proportion)	10%	20%	7
Transition satisfaction	50%	70%	NA
24-month LTFU	25%	15%	10

For the provider and adolescent IDIs, we will select healthcare providers and adolescents from ATP-implementing clinics for individual interviews. Clinics will be purposively selected from among all ATP-implementing clinics. We will purposively select clinics for interviews based on performance, including high and low performing sites as appropriate based on the outcome of the intervention. If the majority of clinics do well, we will purposively select a higher proportion of low performing clinics to understand why they had challenges. If the majority of the clinics do poorly, we will purposively select a higher proportion of high performing clinics to understand how they succeeded.

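### Protocol 11a (Aim 3) contradicts itself on cluster size: 20% of 500 clients is 100 per clinic, yet it prints 200 per clinic with 1000 per arm, and Table 8 rests on 200 per clinic

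*Combined protocol and SAP*

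**What the plan says.** Section 11a of the protocol, Aim 3, starts from "20% of clients being between 10-24 years old and each clinic having at least 500 active clients" and concludes: "we anticipate 200 eligible clients per clinic, for a total of 1000 eligible clients per randomization arm".

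It then splits the clinic total into two age bands: "We assume that 100 of these eligible clients will be aged 6-15" and "We assume that 100 of these eligible clients will be aged 15-24 years". From the older band it derives 20 clients per clinic, or 200 per arm, who could be eligible to transition.

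Table 8 heads each arm in each of its two age bands "N=1000 (100/clinic)". It lists the clinics per arm needed for 80% power at alpha 0.05, with a between-cluster coefficient of variation of 0.3. The trial has 10 clinics per arm.

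Elsewhere, Table 3 (section 5b) sets a minimum of 2000 clients aged 6-24 per arm. Table 4 plans up to 4000 records, 2000 per arm. The SAP finalized in 2020 has separate power tables for transition readiness and for proportions, both at an average cluster size of 50 and an ICC of 0.2.

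**The concern.** The sentence in 11a fails twice. Its inputs do not give 200 per clinic, and 200 per clinic over 10 clinics does not give 1000 per arm. The arm total of 1000 agrees with the inputs; the 200 agrees with the age split, Table 8 and Table 3.

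Cluster size is an input to every clinic count in Table 8. If the 20% and 500 are the real planning basis, the table uses twice the cluster size that they support. At stake are whether the printed counts can be relied on and whether 10 clinics per arm still give 80% power in every row.

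**Working it through.** **Inputs.** From 11a: 20%, 500 clients, 200 per clinic, 1000 per arm, alpha 0.05, 80% power, coefficient of variation k = 0.3, 10 clinics per arm. From Table 8: 100 per clinic per band, and the rates below.

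**Clinic and arm totals.**
- 0.20 × 500 = 100 per clinic; 100 × 10 = 1000 per arm.
- 200 × 10 = 2000 per arm.
- To reach 200 per clinic: 200 / 0.20 = 1000 clients per clinic, or 200 / 500 = 40% in the age range.
- Table 8: 100 + 100 = 200 per clinic; 1000 + 1000 = 2000 per arm.

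**Reproducing Table 8.** The protocol names no formula. The standard one for an unmatched cluster trial with proportions (Hayes-Bennett) is

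c = 1 + (1.96 + 0.84)² × V / (p0 − p1)², where V = p0(1−p0)/m + p1(1−p1)/m + k²(p0² + p1²).

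Rounded up, with two-sided alpha and m = 100, it matches all 11 rows for which both rates are legible. Table 8 was therefore built on 100 per clinic per band.

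**Repeating it at m = 50** (100 per clinic, split equally as 11a splits its 200). Power at c = 10 is Φ(√[9(p0 − p1)²/V] − 1.96).

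| Row | Printed clinics | m = 100 | m = 50 | Power at 10 clinics, m = 100 | Power at 10 clinics, m = 50 |
|---|---|---|---|---|---|
| Disclosure started 50 v 80% | 9 | 9 | 9 | 87.3% | 85.7% |
| Disclosure started 50 v 90% | 6 | 6 | 7 | 96.8% | 96.4% |
| Disclosure started 50 v 100% | 5 | 5 | 5 | 99.3% | 99.2% |
| Disclosure complete 30 v 50% | 8 | 8 | 9 | 89.2% | 85.3% |
| Disclosure complete 30 v 70% | 4 | 4 | 4 | 99.9% | 99.8% |
| LTFU 20 v 10%, younger band | 7 | 7 | 9 | 94.8% | 86.8% |
| Transition discussed 20 v 40% | 6 | 6 | 7 | 98.1% | 96.1% |
| Transition discussed 20 v 60% | 3 | 3 | 4 | 100% | 100% |
| Transition discussed 50 v 100% | 5 | 5 | 5 | 99.3% | 99.2% |
| Transition complete 10 v 20% | 7 | 7 | 9 | 94.8% | 86.8% |
| LTFU 25 v 15%, older band | 10 | 10 | 12 | 82.3% | 71.9% |

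Seven printed counts are too low at m = 50. Six of the corrected counts still fit within 10 clinics.

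**The row that does not fit (25 v 15%).**
- Binomial part: 0.25 × 0.75 + 0.15 × 0.85 = 0.315. Between-clinic part: 0.09 × (0.0625 + 0.0225) = 0.00765.
- m = 100: V = 0.00315 + 0.00765 = 0.0108; c = 9.48, so 10.
- m = 50: V = 0.0063 + 0.00765 = 0.01395; c = 11.95, so 12.
- Power at 10 clinics, m = 50: Φ(√(0.09 / 0.01395) − 1.96) = 71.9%. A non-central t check gives 71.7%; design-effect variants give 71-78%.
- Setting power to 80% at 10 clinics and solving for m gives 82.5, so about 83 per clinic in the older band.

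**The case against.** The strongest reply is that 200 per clinic may be the intended figure. Table 3 makes 2000 per arm a minimum, Table 4 allows 2000 records per arm, and the 100 + 100 split with its 20 per clinic and 200 per arm all follow from 200. The 1000 might even be meant per age band, as in Table 8, although the sentence does not say so. This stands: the documents do not show that 200 is the mistake. It does not remove the contradiction, because 200 still does not follow from 20% of 500.

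Second, 500 is a floor and the 20% is called conservative. The 20% also covers ages 10-24, while the younger band in the text starts at 6, so children aged 6-9 lie outside it. Larger clinics could reach 83 in the older band; at 20% and an equal split that takes 83 × 2 / 0.20 = 830 clients per clinic. This also stands, and makes the power loss conditional. Against it, Table 3 admits clinics with just over 300 clients and expects 50-500 clients aged 6-24 in each.

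Third, the affected row is minor. Loss to follow-up is not among the three effects that 11a names when it claims sufficient power, retention is a secondary outcome, and 11a expects adjustment for baseline to add power. The 2020 SAP makes transition readiness primary, with 12-month follow-up and power tables already at cluster size 50. All of this limits the consequence. Section 11a nevertheless remains in the document as a stated basis for the trial's size.

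**Conclusion.** The contradiction in 11a is certain and needs no outside fact. Which input is wrong cannot be decided from the documents.

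A reader might infer that 200 is simply an error for 100, that Table 8 therefore rests on a doubled cluster size, and that the trial is underpowered. The documents do not support that. Several places agree with 200 per clinic, and even at 50 per band the three effects named in the text (30 to 50%, 50 to more than 80%, 10 to 20%) keep 85-87% power with 10 clinics.

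The supported conclusion is conditional. If 20% of 500 is the planning basis, seven clinic counts in Table 8 are too low and one row, LTFU 25 v 15% at ages 16-24, falls from about 82% to about 72% power. It keeps 80% only if the older band averages at least about 83 per clinic. This rests on the equal age split, on k = 0.3, and on the formula inferred from its exact match to Table 8. The 10 v 20% figure also follows Table 8 in counting the whole older band, not only the fifth that 11a says could be eligible to transition; that is a separate question.

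**What to change.** Decide the planning figure, then align 11a (including the 20 per clinic and 200 per arm eligible to transition), Table 3 and Table 8 with it.

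- **If 200 per clinic is expected:** state the assumption that yields it (about 1000 active clients per clinic, or 40% in the age range), name the age range it covers, and print 2000 per arm. Table 8 then needs no change on this point.
- **If 20% of 500 is the basis:** print 100 per clinic and 1000 per arm, with about 50 per band per clinic (500 per band per arm). Correct the figures derived from 100 per band: 20% of 50 is 10 per clinic, or 100 per arm, eligible to transition. Reconcile Table 3's minimum of 2000. Recompute Table 8, and state about 72% power for the 25 v 15% row at 10 clinics, with the 83-per-clinic condition for 80%.

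In either case, add a sentence noting that the 2020 SAP has its own power tables. The cost is wording and one or two tables; under the second option one row's stated power becomes less favourable. No extra clinics and no change to data collection are proposed.

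### Section 11a, Aim 3: two of the three power contrasts do not start from the control rates assumed just above them, and the transition rows use 100 clients per clinic where the text allows 20

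*Combined protocol and SAP*

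**What the plan says.** The Aim 3 part of protocol section 11a first lists assumptions. For clients aged 6-15, 100 per clinic, "the rate of complete disclosure will be 15% in the control clinics based on our prior studies and the literature", and the same bullet adds that prevalence rises with each year of age. For clients aged 15-24, again 100 per clinic, it takes 20 per clinic (200 per arm) as still in pediatric care and able to transition. Over two years, "we anticipate that in the control arm 20% will transition and 10% will transition effectively".

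The next paragraph claims sufficient power for "an increase in proportion of adolescents with disclosure from 30% to 50%, an increase in proportion who initiate transition from 50% to >80" per cent, and for "an increase in proportion with effective transition from 10% to 20" per cent. On the inputs it says: "This assumes alpha of 0.05, 80% power, and a conservative estimate of the coefficient of variation of 0.3".

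Table 8 is headed ages 10-15 and 16-24, with 100 clients per clinic in each band. Its complete-disclosure rows all have a 30% control rate. Its only 50% versus >80% row is *Disclosure process started* (9 clinics). The *Transition discussed* rows are 20% vs 40%, 20% vs 60% and 50% vs 100%. *Transition complete* is 10% vs 20% (7 clinics).

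**The concern.** A power statement should follow from the assumptions that introduce it. Here the disclosure control rate doubles from 15% to 30%, and the transition rate goes from 20% to 50%, with no reason given. The transition-initiation claim has no transition row behind it in Table 8. A reader cannot tell which control rates the 10 clinics per arm were chosen for.

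This matters because protocol section 3 still names disclosure and effective transition within the Aim 3 primary outcome, and 11a is the only power justification for them. In a cluster design, the clinics needed depend on the control rate, on the intervention rate and on the number of clients per clinic who can have the event. All three have to be settled before the claim can be checked.

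**Working it through.** **Inputs.** From 11a: alpha 0.05, power 80%, between-clinic coefficient of variation k = 0.3, 10 clinics per arm. Clients per clinic m = 100 (Table 8) or 20 (the transition bullet). Sidedness is not stated; two-sided alpha reproduces the table.

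**Formula.** The unmatched cluster formula for two proportions (Hayes-Bennett):

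v = p0(1−p0)/m + p1(1−p1)/m + k²(p0² + p1²)

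clinics per arm c = 1 + 7.849 × v/(p0−p1)², where 7.849 = (1.960 + 0.842)²

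power with 10 per arm = Φ(√[9(p0−p1)²/v] − 1.960)

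**Step 1. Reproduce Table 8 (m = 100).**

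For 30% vs 50%: v = 0.0046 + 0.0306 = 0.0352, so c = 1 + 7.849 × 0.0352/0.04 = 7.91, giving 8 as stated.

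| Contrast | c | Table 8 |
|---|---|---|
| 50 vs 80 | 8.34 | 9 |
| 50 vs 90 | 5.85 | 6 |
| 50 vs 100 | 4.61 | 5 |
| 30 vs 70 | 3.77 | 4 |
| 20 vs 40 | 5.32 | 6 |
| 20 vs 60 | 2.96 | 3 |
| 10 vs 20 | 6.49 | 7 |
| 25 vs 15 | 9.48 | 10 |

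Each agrees after rounding up. The third complete-disclosure row cannot be checked, because its intervention rate is not legible in the available text.

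**Step 2. Change only the control rates (m = 100).**

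| Contrast | v | c, rounded up | Power with 10 |
|---|---|---|---|
| Disclosure as stated, 30 vs 50 | 0.0352 | 8 | 89.2% |
| From 15%, same absolute gain, 15 vs 35 | 0.0166 | 5 | 99.7% |
| From 15%, same relative gain, 15 vs 25 | 0.0108 | 10 | 82.3% |
| Initiation as stated, 50 vs 80 | 0.0842 | 9 | 87.3% |
| From 20%, same absolute gain, 20 vs 50 | 0.0302 | 4 | 99.9% |
| From 20%, same relative gain, 20 vs 32 | 0.0166 | 11 (10.04) | 79.8% |

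**Step 3. Use the 20 eligible clients per clinic (transition outcomes).**

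- 20% vs 40%: v = 0.0200 + 0.0180 = 0.0380, c = 1 + 7.849 × 0.0380/0.04 = 8.46, so 9 clinics; power with 10 is 86.8%.
- 10% vs 20%: v = 0.0125 + 0.0045 = 0.0170, c = 1 + 7.849 × 0.0170/0.01 = 14.34, so 15 clinics; power with 10 is Φ(2.301 − 1.960) = 63.3%.
- With 10 clinics per arm, the smallest intervention rates detectable with 80% power are about 23% from 10% and about 38% from 20%.

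**Step 4. Which denominator do the transition rates belong to?** If 100 per clinic were the base, a control rate of 20% would be 20 clients, which is every eligible client. An effective-transition rate of 20% in the intervention arm would also require every eligible client to succeed. The rates therefore make sense only among the 20.

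**The case against.** Several points on the other side stand.

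- The table is not miscalculated. Step 1 reproduces it, so the defect is in inputs and labels. Table 8 also already holds two rows from a 20% control rate.
- The age bands differ. Disclosure rises with age by the protocol's own statement, so a higher rate at 10-15 than at 6-15 is expected. This may explain part of the gap. With clients spread evenly over the ten single years 6-15, 30% in the six years 10-15 gives at least 0.6 × 30% = 18% overall, even if nobody younger is disclosed. The two figures agree only if at most half the clients are 10 or older. The documents neither give the age mix nor offer this explanation. Nor does the bullet say whether 15% is a baseline or an end-of-study rate.
- The 50% to >80% contrast is probably a label slip for disclosure process started. Reading the assumed 20% who transition as the counterpart of initiating transition is an inference, supported by the paired 10% who do so effectively. *Transition discussed* could apply to all 100 clients; transition itself could not.
- 11a expects baseline adjustment to reduce heterogeneity. That would help, but it acts on k only. For 10% vs 20% at 20 per clinic, even k = 0 gives c = 1 + 7.849 × 0.0125/0.01 = 10.81, so 11 clinics.

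A reader might infer that the mismatched control rates leave the trial underpowered, or that none of the stated power applies. The documents support neither. Step 2 gives more power for the same absolute gains and about 80% for the same relative gains, and the third contrast does start from its assumed rate.

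**Conclusion.** The inconsistency is real and limited to two of the three contrasts: disclosure (30% used, 15% assumed) and initiation of transition (50% used, 20% assumed). Correcting the control rates alone, at 100 per clinic, does not overturn 10 clinics per arm. Which intervention rate to pair with a lower control rate is a choice that the protocol does not make, so both the absolute and the relative readings are shown.

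The claim that weakens is the one whose control rate is consistent. Effective transition from 10% to 20% has about 63% power with 10 clinics per arm at 20 eligible clients per clinic, against 94.8% at the 100 used in Table 8.

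These results assume two-sided alpha, k = 0.3, and the bullet's 20 eligible clients per clinic. The disclosure results also assume 100 clients per clinic in that band.

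The point concerns the protocol's Aim 3 power statement. The 2020 SAP makes the transition readiness score primary, gives it a separate power table (ICC 0.2, average cluster size 50), and lists full disclosure and post-transition retention as exploratory in its summary. Nothing here bears on that table.

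**What to change.** In section 11a and Table 8:

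1. State one control rate of complete disclosure, for one age band and one time point, and recompute the disclosure rows from it. If 15% and 30% are both intended, say that they differ by age or time and give the age mix that reconciles them.
2. Relabel the 50% to >80% contrast as disclosure process started, or replace it with a transition contrast from the 20% control rate.
3. Compute the transition-initiation and transition-complete rows with 20 eligible clients per clinic: 9 clinics for 20% vs 40%, and 15 for 10% vs 20%. If 100 per clinic is meant, justify that denominator against the bullet.
4. Restate the effective-transition claim, either as about 63% power for 10% vs 20% or as a detectable rate of about 23% with 80% power, at 10 clinics per arm.
5. Add a sentence saying which document's power statement governs, since the SAP has moved the primary endpoint.

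The cost is redrafted text and recomputed table rows; no new data are needed. Step 4 does change what the protocol can claim for effective transition. If 80% power for 10% vs 20% is still wanted, 10 clinics per arm do not provide it on these inputs.

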Approach: *We will randomize 20 clinics to receive the ATP or no intervention (SOC) and compare disclosure and appropriate transition using pre-specified milestones among a group of children and adolescents with heterogeneous ages. During early implementation, we will monitor fidelity to the intervention using modified plan-do-study-act (PDSA) cycles. We will track implementation outcomes and factors influencing implementation during the initial ATP implementation phase (6 months). During this time, the study team will discuss and support changes to refine the tool as needed at each facility. Following the initial implementation period, HCWs will take part in focus group discussions to share their suggestions for optimizing the transition tool based on their experience. Understanding personal experiences with the tool will provide an opportunity for lessons learned and continued refinement of the intervention. At the end of the study, we will qualitatively evaluate acceptability, appropriateness and feasibility of the ATP by conducting interviews and FGDs with all HCWs from implementing sites and adolescents from a sub-set of intervention sites, purposively selecting to include participants from high and low performing facilities. We will also conduct pre-trial and post-trial surveys with adolescents and HCWs to quantitatively assess acceptability, appropriateness, feasibility of the ATP and implementation intervention fidelity. At 6-monthly intervals, we will collect readiness assessment information from adolescents in participating clinics.*

SECTION 3: STUDY OUTCOMES

Aim 1

- Prevalence of transition
- Age at transition
- Co-factors for retention
- Age at disclosure
- Co-factors of disclosure
- Individual level co-factors of effective transition
- Facility level co-factors of effective transition

Aim 2

- Adapted transition tool

Aim 3

- The primary outcome is **disclosure** among non-disclosed adolescents and **effective transition and transition readiness** among disclosed adolescents

- Disclosure will be defined as no, partial or complete disclosure. Time to disclosure and age at disclosure will also be assessed.
- Effective transition with retention in care will be defined as completing a visit on the adult day or completing a visit without a caregiver and repeat visits continuing for at least 6 months after transition.
- Transition readiness will be defined as change in response to readiness assessment questions administered every 6 months

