We will enroll 20 facilities to participate in the cluster RCT. The intervention will involve working with and training HCWs at selected facilities and abstracting routinely collected programmatic data for HIV-infected children, adolescents and young adults aged 6-24 years attending the selected clinics (Table 3). We will also routinely abstract data from intervention tools being used at the facilities. We anticipate including up to 200 HCWs per intervention arm in the HCW training and intervention implementation and up to 2000 adolescents per arm. We will also enroll 400 adolescents and 200 HCWs to complete pre-trial surveys and 400 adolescents and 200 HCWs to complete post-trial surveys. HCWs from implementing sites will also participate in repeated surveys and planning meetings twice per month during the first 6 months of implementation of the ATP. We will conduct semi-structured interviews with up to 96 adolescents and 60 HCWs from all clinics included in the intervention arm of the trial. We will also complete FGDs with all HCWs from implementing facilities at 6 months into and at the end of the trial. At 6-monthly intervals, we will collect readiness assessment data from caregivers of children and adolescents who have not yet reached full disclosure, and adolescents and young adults ages 10-24 years who have attained full disclosure.

Program data abstraction: We will abstract program level data at baseline, and throughout the RCT to assess outcomes. Table 3 summarizes enrollment characteristics and data collection tools in the RCT arms.

Table 3: Details of cluster RCT design, enrollment and data collection

	Control arm	Intervention arm
Required Facility Characteristic	>300 clients in HIV care	>300 clients in HIV care
Estimated number of clients aged 6-24 per clinic	50-500	50-500
Minimum number of clients aged 6-24 per RCT arm	2000	2000
Procedures	Standard clinic procedures	Adolescent transition package
Disclosure checklist	√	√
Transition checklist	√	√
Process indicators	-	Disclosure milestones Transition milestones HCW, caregiver and client satisfaction
Maximum number of adolescents completing pre-trial surveys	200	200
Maximum number of HCWs completing pre-trial surveys		200
Maximum number of HCWs participating in repeated surveys and planning meetings		200
Maximum number of HCWs participating FGDs at 6 months		200
Maximum number of adolescents completing transition readiness assessment form	2000	2000

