Recruitment Scripts:

Study Activity	Recruitment Script
Aim 1`	
Facility Survey	Facility Survey Recruitment Script
Aim 2	
Adolescents in HIV care (48 not completed transition, 48 transitioned)	NA
	Caregiver recruitment script for adolescent IDI and FGD
	Adolescent recruitment script
Caregivers	Caregiver recruitment script
Policy makers	Policy maker/Admin/HCW recruitment script
HCW/Administrator	Policy maker/Admin/HCW recruitment script
Working group	HCW recruitment script for Workshop
Aim 3	
Pre-Trial surveys	Adolescent Recruitment Script*
Implementation Activities	HCW IS Activities Recruitment Script
Post-trial IDI	NA
	Adolescent recruitment script*
	Caregiver recruitment script*
	HCW recruitment script*
Implementation FGDs	HCW FGD Recruitment Script
Transition readiness	Adolescent recruitment script*
Disclosure readiness	Caregiver recruitment script
Post-trial surveys	Adolescent recruitment script*
	HCW recruitment script*

*Same as aim 2 document

ATTACH STUDY ANALYSIS PLAN (Finalized 2.13.2020)

SUMMARY

Study Purpose: To determine whether an adolescent transition package (with transition and disclosure tools) improves **mean transition readiness** among HIV positive adolescents in care in Kenya.

Study Design: Cluster randomized trial

Study Population and Sites:

Population:

- HIV-positive adolescents and youth between the ages of 10 and 24

Sites:

- 20 HIV clinics in Nairobi, Nakuru, Homabay and Kajiado, Kenya

Study Duration: Estimated 18 months total (enrollment and 1-year follow-up)

Randomization: 10 clinics randomized to intervention sites and 10 to control.

Intervention:

Adolescent Transition Package (ATP): The ATP will consist of a validated disclosure booklet and disclosure tracking tool, and a HCW administered transition booklet and transition tracking logs, implemented in intervention sites. HCW in intervention sites will be trained on implementation of the ATP with continued support for the clinic in the first 3 months of the intervention. In control sites, parallel data collection for primary outcomes will be conducted.

Primary endpoints: Transition readiness

Secondary endpoints: Overall clinic retention and overall viral suppression

Exploratory outcome: % with full disclosure, Time to full disclosure, Post transition retention

DATA ANALYSIS

Primary outcome: transition readiness among HIV positive adolescents age 15-24

- a. Transition readiness score overall (all domains)
- b. Treatment literacy readiness score

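### The protocol's 80% power for effective transition (10% vs 20%) rests on 100 adolescents per clinic, but only 20 per clinic are said to be eligible; 20 per clinic gives about 63%

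*Combined protocol and SAP*

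**What the plan says.** Protocol section 3 names effective transition as part of the Aim 3 primary outcome and defines it as "completing a visit on the adult day or completing a visit without a caregiver", with repeat visits continuing for at least 6 months.

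Protocol section 11a (Aim 3) assumes 100 clients aged 15-24 per clinic. Of these, "20% (n=20) will be receiving care in a pediatric program and could be eligible to transition (200 per RCT arm"). It expects that over 2 years 20% of the control arm will transition and 10% will do so effectively. It then claims sufficient power with 10 clinics per arm for "an increase in proportion with effective transition from 10% to 20" per cent, at alpha 0.05, 80% power and a coefficient of variation of 0.3. It adds: "Heterogeneity between clusters is expected to decrease with control for baseline testing rates, leading to increased power beyond that which is noted above".

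Table 8 sets the age 16-24 block at 100 per clinic (1000 per arm) and lists 7 clinics per arm for *Transition complete*, 10% vs 20%.

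Two other statements in section 11a are affected:
- **Volumes.** From 20% of at least 500 clients per clinic, "we anticipate 200 eligible clients per clinic, for a total of 1000 eligible clients per randomization arm". Table 3 gives 2000 for "Minimum number of clients aged 6-24 per RCT arm".
- **Label.** The power statement includes "an increase in proportion who initiate transition from 50% to >80" per cent.

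The analysis plan of February 2020 states "Primary endpoints: Transition readiness" and lists post-transition retention as exploratory.

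**The concern.** Power for a proportion depends on the number of people who can have the event. Section 11a gives that number as 20 per clinic, and Table 8 then uses one five times larger for the same outcome. If 20 is right, a component of the protocol's primary outcome has clearly less than the stated 80% power. A null result for transition could then be read as evidence of no effect when the trial was too small to show a doubling.

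**Working it through.** **Inputs (section 11a and Table 8).** Control proportion p0 = 0.10; intervention proportion p1 = 0.20; alpha 0.05; power 80%; CV = 0.3; 10 clinics per arm; m = 100 per clinic (Table 8) or m = 20 (text). The documents name no formula and do not say whether alpha is two-sided.

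**Formula.** The standard coefficient-of-variation (Hayes-Bennett) formula for an unmatched cluster trial, with two-sided alpha:

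c = 1 + 7.849 × V / (p0 − p1)², where V = p0(1 − p0)/m + p1(1 − p1)/m + CV²(p0² + p1²).

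Power with c clinics per arm = Φ(√[(c − 1)(p0 − p1)²/V] − 1.96).

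**Reproducing Table 8 at m = 100.** V = 0.0009 + 0.0016 + 0.09 × 0.05 = 0.0070, so c = 1 + 7.849 × 0.70 = 6.49, rounded up to 7 as printed. The formula also matches every other complete row:

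| Proportions (%) | Formula | Table 8 |
|---|---|---|
| 50 vs 80 | 8.34 | 9 |
| 50 vs 90 | 5.85 | 6 |
| 50 vs 100 | 4.61 | 5 |
| 30 vs 50 | 7.91 | 8 |
| 30 vs 70 | 3.77 | 4 |
| 20 vs 10 | 6.49 | 7 |
| 20 vs 40 | 5.32 | 6 |
| 20 vs 60 | 2.96 | 3 |
| 25 vs 15 | 9.48 | 10 |

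Dropping the +1 (5.49, so 6) or using one-sided alpha (5.33, so 6) does not give the printed 7. The method and the cluster size of 100 are therefore well identified.

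**Same calculation at m = 20.** V = 0.0045 + 0.0080 + 0.0045 = 0.0170, so c = 1 + 7.849 × 1.70 = 14.34, or 15 clinics per arm. With 10 per arm, √(9 × 0.01/0.0170) = 2.301, and Φ(2.301 − 1.96) = 0.633.

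| At risk per clinic | Clinics per arm for 80% | Power with 10 per arm |
|---|---|---|
| 100 | 6.49 (7) | 95% |
| 50 | 8.46 (9) | 87% |
| 36 | 9.98 (10) | 80% |
| 30 | 11.07 (12) | 75% |
| 20 | 14.34 (15) | 63% |

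With 10 clinics per arm and 80% power, the detectable rise from 10% is to about 17% at m = 100 and to about 23% at m = 20.

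**Baseline adjustment at m = 20.** Power is 70% at CV 0.2, 75% at CV 0.1 and 76.5% at CV 0 (10.81, so 11 clinics).

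**Other methods at m = 20, CV 0.3.** A t test on 18 df gives 63.1%; omitting the +1 gives 67.9%; a design effect of 1.30 (intraclass correlation 0.09 × 0.15/0.85 = 0.016) gives 69.1%; one-sided alpha gives 74.4%. All are below 80%.

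**Could 10% and 20% be shares of all 100?** Then 20% is 20 of 100, so every eligible adolescent in the intervention clinics would have to transition effectively. The assumed 20% of control clients who transition would likewise be all of those eligible.

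**Volumes.** 0.20 × 500 = 100 per clinic, not 200; 200 × 10 = 2000 per arm, not 1000.

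**Label.** No transition row in Table 8 has 50% vs 80%. That pair is in the *Disclosure process started* row.

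**The case against.** The strongest reply is that 20 is not a firm denominator. It counts those in a pediatric program, while section 3 also accepts a visit without a caregiver. Section 1a describes clinics where the same team sees everyone and transition simply means attending independently. Clients may also age into the 15-24 group over 2 years. With a somewhat larger number at risk and some gain from baseline adjustment the claim could be met: m = 30 with CV 0.2 gives 84% power, and m = 36 with CV 0.2 gives 89%. Without the +1 term, m = 20 and CV 0 gives 80.7%.

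This shows how the claim might be rescued, but the protocol does not make the case. It gives no count of adolescents eligible to transition other than 20; the 100 in Table 8 is the size of the age band. It gives no figure for the reduction in CV. The 80.7% needs both zero between-clinic variation and a formula that does not reproduce Table 8. If a larger number is right, the sentence giving 20 is wrong and still needs correcting.

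Three points on scope stand:
- The analysis plan has its own power table for transition readiness, so the shortfall does not touch its primary analysis.
- The figure of 200 per clinic agrees with the age-band bullets, Table 8 and Table 3. The likelier errors are the 1000 per arm and the derivation from 20% of 500.
- The mislabelled 50% vs 80% claim survives as a power statement: even at m = 20 it needs 9.77, so 10 clinics, with 81% power.

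**Conclusion.** The point holds and should be fixed. The protocol's stated 80% power for effective transition is not delivered by the only eligible number it gives. On its own assumptions, with 20 at risk per clinic, power is about 63% (63-69% across the two-sided methods tried), and 15 clinics per arm would be needed against 10 randomised.

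This rests on CV 0.3, two-sided alpha and m = 20. It would change if at least about 36 per clinic were shown to be at risk, or a smaller increase in that number were combined with a justified lower CV. The consequence is confined to the protocol's power statement and to how a null transition result is interpreted.

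**What to change.** 1. Recompute the *Transition complete* row of Table 8 with the number actually at risk: 20 per clinic, unless a larger figure under the section 3 definition is stated and justified.
2. In section 11a, state that 10 clinics per arm give about 63% power for 10% vs 20%, or that the detectable rise at 80% power is from 10% to about 23%. If baseline adjustment is relied on, give the assumed CV.
3. Reconcile the per-clinic and per-arm volumes with Table 3. Only if 100 per clinic proves correct, recompute the other rows at about 50 per age band (assuming an equal split). Those eligible to transition would then be about 10 per clinic (20% of 50), with power about 42%.
4. Relabel the 50% to >80% claim to match the Table 8 row with those values.
5. Add a sentence that the analysis plan's primary endpoint is transition readiness, with its own power table, and that post-transition retention is exploratory.

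The cost is protocol wording and one recomputed row. No clinics, participants or data are added; the stated power for effective transition becomes less favourable.
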